9.1.1.2 Rescreening

Subjects may be rescreened once. If a subject is rescreened, the subject will provide informed consent and assent (as applicable), and all screening assessments will be repeated, except for:

- *CFTR* genotyping
- Ophthalmologic examination (if performed within 3 months before the date of informed consent)

If a subject is rescreened, a new screening window will begin when the first rescreening assessment has been initiated.

9.1.1.3 Extension of Screening Period Window

A subject may have the Screening Period window extended by 2 weeks for the following reasons:

- Repetition of the Screening Period assessments (Section 9.1.1.1)
- Unexpected operational or logistic delays, or to meet the eligibility criteria
- Scheduling of ophthalmologic examination (Section 11.4.5)

9.1.2 Treatment Period

Treatment Period assessments are listed in Table 3-2.

The Treatment Period will last approximately 48 weeks. Study drug administration details are provided in Section 9.6.

9.1.3 Follow-up

The Safety Follow-up Visit is scheduled to occur 28 (\pm 7) days after the last dose of study drug. The Safety Follow-up Visit is not required for subjects who complete the Week 48 Visit and enroll in the open-label extension safety study, or who transition to a commercially available CFTR modulator regimen, within 28 days after the last dose of study drug.

9.1.4 Early Termination of Treatment

If a subject prematurely discontinues study treatment, an Early Termination of Treatment (ETT) Visit should be scheduled as soon as possible after the subject decides to terminate study treatment. Subjects who prematurely discontinue treatment will also be required to complete the Safety Follow-up Visit.

If the ETT Visit occurs 3 weeks or later following the last dose of study drug, then the ETT Visit will replace the Safety Follow-up Visit, and a separate Safety Follow-up Visit will not be required.

If a subject withdraws from the study and also withdraws consent or assent, no further assessments will be performed. Vertex may retain and continue to use any data and samples collected before such withdrawal of consent or assent.

9.1.5 Lost to Follow-up

A subject will be considered lost to follow-up if both of the following occur:

- The subject misses 2 consecutive study visits (telephone contact, clinic, and/or home health visit) and is subsequently unable to be contacted by telephone (3 documented attempts by telephone within 2 weeks following the second missed visit)
- The subject does not respond within 2 weeks to a registered letter sent after the 3 attempted telephone contacts.

9.1.6 Completion of Study Participation

Completion of study participation for each individual subject is defined as 1 of the following:

- For subjects who complete the Treatment Period and enter an open-label extension safety study within 28 days of the Week 48 Visit: the Week 48 Visit
- For subjects who complete the Treatment Period and do not enter an open-label extension safety study within 28 days of the Week 48 Visit: the Safety Follow-up Visit
- For subjects who prematurely discontinue study drug treatment but do not withdraw consent (and assent, as applicable): the latest of the ETT Visit or Safety Follow-up Visit (if required)
- For subjects who withdraw consent or assent: date of withdrawal of consent or assent, whichever is earlier (Section 9.9)

If subjects are lost to follow-up (Section 9.1.5), the date of completion of study participation will be defined as the date of the last contact.

The end of study is defined in Section 13.2.9.

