9 STUDY IMPLEMENTATION

9.1 Study Design

This is a Phase 3b, open-label study in CF subjects 12 years of age and older with F/MF genotypes and abnormal glucose tolerance ([Figure 9-1](#)). Approximately 60 subjects (F/MF genotypes) will be enrolled, of whom approximately 30 subjects will have IGT and 30 subjects will have CFRD. During the Treatment Period, subjects will be administered ELX/TEZ/IVA for approximately 48 weeks. All subjects will receive ELX 200 mg once daily (qd)/TEZ 100 mg qd/IVA 150 mg every 12 hours (q12h).

Figure 9-1 VX19-445-117 Study Design

ELX: elexacaftor; CFRD: CF-related diabetes; CGM: continuous glucose monitoring; IVA: ivacaftor; N: total sample size; TEZ: tezacaftor

^a On Day -7, a CGM sensor will be inserted subcutaneously to assess baseline blood glucose levels for 7 days prior to the first dose of study drug in subjects with CFRD.

^b Subjects who complete the visits in the Treatment Period, regardless of whether they are on a treatment interruption, will be offered the opportunity to enroll in an open-label extension safety study evaluating ELX/TEZ/IVA. The Safety Follow-up Visit is not required for subjects who complete the Week 48 Visit and have enrolled in an open-label study within 28 days after the last dose of study drug.

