13.1.1.3 Documentation of Adverse Events

All AEs will be collected from the time the ICF is signed until the subject completes study participation, as defined in Section 9.1.6

All subjects and their parents or legal guardians will be queried, using nonleading questions, about the occurrence of AEs at each study visit. When possible, a constellation of signs and/or symptoms will be identified as 1 overall event or diagnosis. All AEs for enrolled subjects will be recorded in the case report form (CRF) and source document. AEs for subjects who are screened but not subsequently enrolled will be recorded only in the subject's source documents. The following data will be documented for each AE:

- Description of the event
- Classification of “serious” or “nonserious”
- Date of first occurrence and date of resolution (if applicable)
- Severity
- Causal relationship to study drug(s)
- Action taken
- Outcome
- Concomitant medication or other treatment given

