13.1.2.2 Reporting and Documentation of Serious Adverse Events

All SAEs that occur after obtaining informed consent through the Safety Follow-up Visit, regardless of causality, will be reported by the investigator to Vertex global patient safety (GPS) **within 24 hours of identification**. In addition, all SAEs that occur after the Safety Follow-up Visit and are considered related to study drug(s) will be reported to Vertex GPS **within 24 hours of identification**.

For SAEs that occur after obtaining informed consent through the Safety Follow-up Visit, the SAE Form will be completed for new/initial events as well as to report follow-up information on previously reported events. Investigators are asked to report follow-up information as soon as it becomes available to ensure timely reporting to health authorities.

Please send completed SAE Forms to Vertex GPS via:

Email: [contact] (preferred choice)

[contact]

For technical issues related to submitting the form, contact [contact]

SAEs that occur after the Safety Follow-up Visit and are considered related to study drug(s) will be recorded on the Vertex Clinical Trial Safety Information Collection Form (hereafter referred to as the “SAE Form”) using a recognized medical term or diagnosis that accurately reflects the event. SAEs will be assessed by the investigator for relationship to the investigational study drug(s) and possible etiologies. On the SAE Form, relationship to study drug(s) will be assessed only as related (includes possibly related) or not related (includes unlikely related), and severity assessment will not be required. For the purposes of study analysis, if the event has not resolved at the end of the study reporting period, it will be documented as ongoing. For purposes of regulatory safety monitoring, the investigator is required to follow the event to resolution and report the outcome to Vertex using the SAE Form.

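### Completion of participation is tied to a waived visit for subjects moving to a commercial modulator, and AE collection for extension entrants stops at Week 48 even when entry is up to 28 days later

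*Protocol*

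**What the plan says.** **Waiver.** Protocol 9.1.3 schedules the Safety Follow-up Visit 28 ± 7 days after the last dose. It drops the visit for Week 48 completers who enroll in the extension, or "who transition to a commercially available CFTR modulator regimen, within 28 days after the last dose of study drug".

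**Completion.** Protocol 9.1.6 divides treatment completers into two groups only. Those who "enter an open-label extension safety study within 28 days of the Week 48 Visit: the Week 48 Visit" form the first. Those who "do not enter an open-label extension safety study within 28 days of the Week 48 Visit: the Safety Follow-up Visit" form the second. Commercial switchers have no bullet of their own and so fall into the second group.

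**Rules that depend on these dates.**
- Protocol 13.1.1.3: "All AEs will be collected from the time the ICF is signed until the subject completes study participation, as defined in Section 9.1.6".
- Protocol 13.1.2.2: "All SAEs that occur after obtaining informed consent through the Safety Follow-up Visit" are reportable whatever their cause. After that visit, SAEs considered related to study drug remain reportable.
- Protocol 12.3.1 and SAP 8.1: the TE period ends at the earlier of 28 days after the last dose and completion of participation. Both documents take completion from Protocol 9.1.6.
- Protocol 9.6.1: the last dose is taken on the evening before the Week 48 Visit.

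**Footnotes.** Table 3-2 footnote c and note b to Figures 2-1 and 9-1 waive the visit for extension entrants only. Note b also offers the extension to subjects who complete the visits "regardless of whether they are on a treatment interruption".

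**The concern.** Completion of participation controls how long AEs are collected, and it is one of the two limits on the TE period, on which SAP 8.4 bases the safety analyses. Safety and tolerability is the secondary objective and a secondary endpoint, so the date should exist and be unambiguous for every exit route.

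For commercial switchers the date is a visit that they need not attend. For extension entrants the date exists, but it can fall up to four weeks before the extension begins. The 28 days are also counted from different starting points in 9.1.3 and 9.1.6. Sites could therefore handle identical subjects differently, and some AEs soon after the last dose might be asked about in neither study.

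**Working it through.** The plan states no figure to reproduce here. The check sets the rules side by side and does the day arithmetic.

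**Inputs.** Week 48 Visit = day 0; last dose = day −1 (9.6.1); Safety Follow-up window 28 ± 7 days after last dose (9.1.3); TE cap 28 days after last dose (12.3.1, SAP 8.1); waiver limit 28 days after last dose (9.1.3); extension-entry limit 28 days from Week 48 (9.1.6).

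**Ordinary completer.**
- Safety Follow-up window: −1 + 21 = day 20 to −1 + 35 = day 34.
- TE cap: −1 + 28 = day 27.
- Waiver limit under 9.1.3: −1 + 28 = day 27. Entry limit under 9.1.6: day 28. The two differ by one day.
- Extension entrant: the TE period ends at day 0, which is 0 − (−1) = 1 day after the last dose. That is 28 − 1 = 27 days short of the cap.
- Gap between the end of AE collection and extension entry: 0 to 28 days under 9.1.6, or 0 to 27 where the 9.1.3 waiver also applies.
- An entrant on day 28 is 29 days past the last dose: complete under 9.1.6, but outside the waiver in 9.1.3.

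| Route after Week 48 | Safety Follow-up Visit | End of AE collection | End of all-causality SAE reporting | TE follow-up after last dose |
|---|---|---|---|---|
| Neither extension nor commercial drug | Required | That visit | That visit | 21 to 28 days |
| Extension | Waived | Week 48 Visit | Tied to the waived visit | About 1 day |
| Commercial modulator | Waived in 9.1.3, not in the footnotes | Tied to the waived visit | Tied to the waived visit | 28 days, no contact scheduled |

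The 21 to 28 days in the first row is the earlier of the visit (21 to 35 days after last dose) and the 28-day cap.

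**Subject on an interruption (illustrative days).** Assume last dose on Day 295, Week 48 on Day 337 (the target day in SAP Appendix A) and extension entry on Day 340.
- Entry is 340 − 337 = 3 days after Week 48, so participation is complete at Week 48 under 9.1.6.
- Entry is 340 − 295 = 45 days after the last dose, more than 28, so the visit is not waived under 9.1.3.
- The visit window is Day 295 + 21 = 316 to Day 295 + 35 = 330, already past at Week 48.
- The TE period ends at the earlier of Day 295 + 28 = 323 and Day 337, that is Day 323, which is 14 days before Week 48. The Week 44 contact (44 × 7 + 1 = Day 309) and the Week 48 Visit both ask about AEs, so no treatment-emergent AE is lost.

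The visit rules conflict for this subject, but the TE data are complete.

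**The case against.** The case for leaving the text alone has several sound parts.

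- **SAE reporting does not stop.** A reader might infer from 13.1.2.2 that all SAE reporting ends at the Safety Follow-up Visit. Only all-causality reporting does. Related SAEs stay reportable, and 13.1.1.7 has each AE followed to a final outcome. This stands.
- **The commercial route keeps a TE limit.** The 28-day cap closes the TE period without a completion date, so the analysis variable is defined. The visit is also not required rather than forbidden, and a missing end date, read literally, leaves collection open. This stands. What remains is an undefined end of collection and reporting, with no scheduled contact.
- **The extension rule is internally consistent.** Sections 9.1.6 and 12.3.1 and SAP 8.1 agree, and the extension protocol may collect AEs from its own consent. So 0 to 28 days is a bound for this protocol alone, and it is 0 for same-day entry.
- **AE incidence.** A reader might infer that AE incidence is understated, particularly for subjects interrupted for safety reasons. The documents do not support this. Coverage by the extension is unknown, the numbers on each route are not given, and the interruption example loses no treatment-emergent AE.
- **Limited consequence.** Safety is descriptive, single-arm and untested (Protocol 12.3.4, SAP 8.4). Unequal follow-up biases no treatment comparison, and the primary endpoint is unaffected.

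None of this reconciles 9.1.3 with 9.1.6, or with the footnotes.

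**Conclusion.** The contradiction is in the current text and should be corrected. For commercial switchers, the ends of AE collection and of all-causality SAE reporting are undefined, and the 28 days that count as treatment-emergent contain no scheduled contact. For extension entrants, AE collection and the TE period under this protocol end about 1 day after the last dose, with a possible gap of 0 to 28 days before entry; AEs in that gap may be missed. Their all-causality SAE limit is also tied to a waived visit. The 28-day anchors differ by one day for an ordinary completer and by more for a subject on an interruption.

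This rests on three conditions: the last dose falls on the evening before Week 48 except in the interruption case; nothing is assumed about AE collection in the extension protocol; and the number of subjects on each route is unknown, so no effect on AE rates can be estimated. The point concerns how safety data are collected and counted, and does not touch the efficacy analysis.

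**What to change.** 1. **9.1.6, commercial route.** Add a bullet with a dated completion event that keeps the 28-day TE period, such as a telephone AE contact about 28 days after the last dose. Because the TE period ends at completion if that comes first, the contact should not fall before day 28. The date of the first commercial dose would be a poor choice, since it could cut this route's TE period to about a day.
2. **9.1.6, extension route.** Define completion as the date of enrolment in the extension, with AEs asked about then, so that collection is continuous.
3. **Anchor.** Count the 28 days from one event in 9.1.3, 9.1.6, Table 3-2 footnote c (which names none) and the figure notes. Check the choice against a subject who is on an interruption at Week 48.
4. **Footnotes.** Add the commercial waiver to Table 3-2 footnote c and to the notes to Figures 2-1 and 9-1.
5. **13.1.2.2.** Tie the all-causality limit to completion of study participation in place of the Safety Follow-up Visit, and keep the rule for related SAEs afterwards.

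The cost is a protocol wording change, one telephone call or AE question per subject on these routes, and slightly more data entry. The TE definition in SAP 8.1 already refers to Protocol 9.1.6 and needs no change.

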9.1.7 Use of Remote Measures

Remote measures may be used for study visits at Week 4 and Week 12 (see Table 3-2). All other visits must be performed in the clinic.

Whenever local regulations or site practice do not allow remote measures, visits will be conducted at the site. However, under extenuating circumstances, remote measures may be implemented (e.g., if a subject is unable to travel to the study site due to safety concerns and/or local restrictions related to COVID-19 or other emerging events). The decision whether to conduct a study visit remotely or in clinic will be at the discretion of the investigator; if the investigator determines that study visits will be conducted remotely, the medical monitor should be notified. Under extenuating circumstances, the Screening visit (including initial consent) and Day 1 visits must still be performed in the clinic.

The following remote measures may be implemented. Additional details can be found in the Study Reference Manual.

- Consent and reconsent may be obtained electronically (or verbally, with follow-up electronic/written confirmation), as allowed by local regulations.
- Study drug may be shipped directly from the site to the subject, as applicable and as allowed by local regulations.
- Under extenuating circumstances, study visits (except Screening and Day 1) may be conducted as in-home visits by qualified personnel. All visits must have a consultation between the subject and investigator (i.e., in person, phone, or telemedicine video conference) within 1 business day after the home health visit, which can be outside the visit window.
- Study assessments may be performed or overseen by qualified personnel conducting the in-home visits.
- Remote monitoring visits may be implemented as applicable (including remote source data verification) and as allowed per local regulations.

9.2 Method of Assigning Subjects to Treatment Groups

This is an open-label study.

9.3 Rationale for Study Elements

9.3.1 Study Design

In patients with CF, IGT (a form of prediabetes) and then CFRD develops progressively, starting as early as age 10, and without known remission.¹⁴ Once the diagnosis of IGT is made, patients have an approximately 4 to 11 × increased risk of developing CFRD over a 3 to 4 year observation period^{15, 16}, at which point insulin treatment is often started. Thus, the diagnoses of IGT and CFRD are considered robust and clinically relevant categories of disease.¹⁶ An open-label study design is therefore appropriate to ascertain the effects of ELX/TEZ/IVA through within-group comparisons over 48 weeks. A 48-week treatment period is expected to be sufficient to determine the maximum treatment effect of ELX/TEZ/IVA on changes in glucose tolerance (OGTT) in CF subjects with IGT or CFRD, and follows a similar open-label study design in which Orkambi was found to improve glucose tolerance in subjects with IGT and CFRD.¹⁷ Due to the known variability in the OGTT in patients with IGT and CFRD, 2 OGTTs at baseline (Screening and Day 1), 1 OGTT at Week 24, and 2 OGTTs at the end of the study (Weeks 36 and 48) will be performed.¹⁸

9.3.2 Study Population

This study will enroll CF subjects with F/MF genotypes, 12 years of age and older. A pivotal Phase 3 study demonstrated efficacy and safety of ELX/TEZ/IVA in CF subjects with F/MF genotypes 12 years of age and older. The F/MF population has the highest incidence of abnormal glucose tolerance, as defined by an OGTT, including IGT and CFRD. This is due to stereotypical progression of pancreatic disease, including blocked acinar ducts, atrophy of the exocrine pancreas, loss of endocrine islets, inflammation, additional genetic factors, and other potential mechanisms as described above. Patients with F/MF genotypes therefore offer a population of patients who are naive to CFTR modulator treatment and have prevalent endocrine disease (IGT/CFRD) that is amenable to investigation.

This study will utilize both the OGTT and CGM to evaluate the effect of ELX/TEZ/IVA on abnormal glucose homeostasis in subjects with CF and F/MF genotypes.

9.3.3 Study Drug Dose

The dose of ELX/TEZ/IVA evaluated in the pivotal Phase 3 study in subjects with F/MF genotypes ≥12 years of age (ELX 200 mg qd/TEZ 100 mg qd/IVA 150 mg q12h) was generally safe and well tolerated and resulted in clinically meaningful improvements compared to placebo in endpoints including ppFEV₁ (LS mean treatment difference of 14.3 percentage points [p<0.0001] for absolute change from baseline) and SwCl (LS mean treatment difference of -41.8 mmol/L [p<0.0001] for absolute change from baseline) through 24 weeks. This dose of ELX/TEZ/IVA is approved in some regions for the treatment of CF and will be used for all subjects enrolled in this study.

9.3.4 Rationale for Study Assessments

The safety assessments are standard parameters for clinical studies in drug development.

An OGTT will be performed to assess changes in glucose levels post-oral glucose challenge, including the 2-hour time point. The OGTT is a standard procedure recommended annually for CF patients by age 10, and any other time CFRD is suspected. CGM will be performed in subjects with CFRD only to assess dynamic, free-ranging changes in capillary glucose levels and for associations with changes in other biomarkers or parameters. Serum biomarkers of glucose homeostasis (insulin, glucagon, incretins) are standard biomarkers for mechanistic studies involving patients with diabetes. Changes in ppFEV₁ have been correlated with glucose control parameters (i.e., CGM)¹⁵, and will be useful to establish extrapulmonary (independent of lung) efficacy, and also confirm a positive drug effect throughout the study. SwCl is a standard pharmacodynamic (PD) assessment for studies involving subjects with CF, and this PD marker in skin can be correlated with pulmonary and extrapulmonary (diabetes-related) endpoints in order to advance the understanding of systemic efficacy of ELX/TEZ/IVA.

9.4 Study Restrictions

Table 9-1 lists prohibited medications. A non-exhaustive list of study prohibitions and cautions for medication will be provided in the Study Reference Manual.

Table 9-1 Prohibited Medications

Medication	Timing of Restriction		Rationale
	Start of Restriction	End of Restriction	
Moderate and strong CYP3A inducers	None allowed within 14 days before the first dose of the study drug on Day 1	None allowed through completion of study participation	ELX, TEZ, and IVA are metabolized extensively via CYP3A4. Therefore, use of moderate and strong inducers and inhibitors of CYP3A, which have the potential to alter the exposure of ELX, TEZ, or IVA, are prohibited.
Moderate and strong CYP3A inhibitors (except ciprofloxacin) ^a	None allowed within 14 days before the first dose of the study drug on Day 1	None allowed through completion of study participation	
CFTR modulators (investigational or approved), except for study drugs	None allowed within 28 days before the first dose of the study drug on Day 1	None allowed until after the last dose of study drug	These agents may confound the results of this study.
Anti-diabetic medications, except for exogenous (subcutaneously injected) insulins	None allowed within 28 days before the first dose of the study drug on Day 1	None allowed until after the last dose of study drug	These agents may confound the results of this study.

CYP: cytochrome P450; ELX: elexacaftor; IVA: ivacaftor; TEZ: tezacaftor

^a Ciprofloxacin is not a moderate CYP3A inhibitor on the basis of results of a drug-drug interaction study conducted with IVA, a sensitive CYP3A substrate (Kalydeco [ivacaftor] US Package Insert).

